6.3.17. Instrumental Measurements Post-Procedure, Pre-Treatment (BASELINE)

Assessments to be taken and recorded as per 6.3.11, 60±15 minutes after completion of the facial peel procedure.

6.3.18. Image Capture (VISIA) Post-Procedure, Pre-Treatment (BASELINE)

Assessments to be taken and recorded as per 6.3.12, 60±15 minutes after completion of the facial peel procedure.

6.3.19. Subject Self-Assessment Post-Procedure, Pre-Treatment (BASELINE)

Assessments to be taken and recorded as per 6.3.13, 60±15 minutes after completion of the facial peel procedure.

6.3.20. Test Product Weighing

The Investigator or designee will weigh the test and washout products using a calibrated mass balance to 2 decimal places (in grams) and will document the measured weight on the eCRF.

6.3.21. Test Product and Test Diary Dispensing. Washout Diary Collection.

The time and date of test product dispensing will be documented on the eCRF. Test product diary will be dispensed and washout diary collected. Subjects randomised to test product will be dispensed a different diary than subjects who are not randomised to test product. The Investigator or designee involved in test product and test diary dispensing must not be involved in any assessments in order to protect the blind.

6.3.22. Supervised Test Product Application Post-Procedure

Subjects randomized to test product (Group I) will be instructed to apply the test product as per the labelled usage instructions immediately after the post-procedure, pre-treatment (baseline) assessments are complete. The Investigator or designee will oversee this initial product application. Group II will not apply any test product. Product application will be recorded on the eCRF and subject diary and must happen at least 30 minutes prior to any further instrumental measurements. The Investigator or designee involved in this step must not be involved in any assessments in order to protect the blind.

 GlaxoSmithKline	Document Name	Protocol 2017-01-08F 20 Day Cream.doc		
	Type	Version	Document Identifier	Effective Date
	eldo_controlled	0.0; CURRENT/Effective/Current/Reviewed	090032d580e2d8a6	07-Jun-2017 01:32:30
	Reason For Issue	Auto Issue		

6.3.23. Instrumental Measurements Post-Procedure, Post-Treatment

Measurements to be taken and recorded as per 6.3.11, 180±15 and 360±15 minutes after completion of the facial peel procedure.

6.3.24. Subject Self-Assessment Post-Procedure, Post-Treatment

Assessments to be taken and recorded as per 6.3.13, 180±15 minutes after completion of the facial peel procedure.

6.3.25. Evaluator (Dermatologist) Assessment Post-Procedure, Post-Treatment

Assessments to be taken and recorded as per 6.3.14, 180±15 minutes after completion of the facial peel procedure.

Subjects will remain at site until at least 5:00 PM to prevent exposure to intense sunlight.

6.4. Visit 4 – 1 day after Visit 3

Subjects will be instructed to arrive at the site prior to 9:00 AM to minimize exposure to intense sunlight.

6.4.1. Current / Concomitant Medication

Any concomitant therapy taken since the last visit and throughout the study will be recorded on the eCRF by the Investigator or designee.

6.4.2. Adverse Events

Adverse events will be assessed by the Investigator or designee and recorded on the eCRF, as per the process detailed in Section 7.

As per Section 7.1, the following does not meet the definition of an adverse event: “Any clinically significant abnormal laboratory findings (if applicable) or other abnormal safety assessments which are associated with the underlying disease, unless judged by the investigator to be more severe than expected for the subject’s condition.” Therefore, the Dermatologist (erythema, edema, dryness, and desquamation) and Subject-self assessment (pain, stinging/burning, itching, tightness, redness, and dryness) grades will only be considered adverse events if they are scored

 GlaxoSmithKline	Document Name	eCRF 20 Day Cream.doc		
	Type	Version	Document Identifier	Effective Date
	eldo_controlled	0.0: Duplicate Effective Date	090032d580e2d8a6	07-Jun-2017 01:32:30
	Reason For Issue	Auto Issue		

as “Severe”, or if the investigator judges them to be more severe than expected in context of the Glycolic Acid treatment procedure.

6.4.3. Continued Subject Eligibility

The Investigator or designee will ascertain whether there have been any deviations from the protocol since the last visit, whether the subject has adhered to the lifestyle restrictions since the last visit and whether, in their opinion, the subject is eligible to continue in the study. Subject Continued Subject Eligibility will be recorded on the eCRF.

6.4.4. Compliance (Diary Review)

Subject diaries will be reviewed by the Investigator or their designee. Subjects who apply the washout products (All subjects) and test product (Group I, only) more or less frequently than twice a day will be considered to have deviated from the protocol and additional/missed applications will recorded on the Deviations Log. The total number of product applications and total number of missed product applications will be recorded on the eCRF.

6.4.5. Washout Products Weighing

The Investigator or designee will weigh the washout products using a calibrated mass balance to 2 decimal places (in grams) and will document the measured weight on the eCRF.

6.4.6. Test Product Weighing

The Investigator or designee will weigh the test product using a calibrated mass balance to 2 decimal places and will document the measured weight on the eCRF.

6.4.7. Instrumental Measurements Post-Procedure, Post-Treatment (24±4 hours after Facial Peel)

Measurements to be taken and recorded as per 6.3.11, 24±4 hours after completion of the facial peel procedure.

6.4.8. Image Capture (VISIA) Post-Procedure, Post-Treatment (24±4 hours after Facial Peel)

Assessments to be taken and recorded as per 6.3.12, 24±4 hours after completion of the facial peel procedure.

 GlaxoSmithKline	Document Name	090032d580e2d8a6 20 Day Cream.doc		
	Type	Version	Document Identifier	Effective Date
	eldo_controlled	0.0; CURRENT Effective Date: CURRENT	090032d580e2d8a6	07-Jun-2017 01:32:30
	Reason For Issue	Auto Issue		

6.4.9. Subject Self-Assessment Post-Procedure, Post-Treatment (24±4 hours after Facial Peel)

Assessments to be taken and recorded as per 6.3.13, 24±4 hours after completion of the facial peel procedure.

6.4.10. Dermatologist Assessment Post-Procedure, Post-Treatment (24±4 hours after Facial Peel)

Assessments to be taken and recorded as per 6.3.14, 24±4 hours after completion of the facial peel procedure.

6.4.11. Supervised Test Product Application

Only subjects in Group I will undergo supervised test product application. The Investigator or designee will oversee application of the test product. Product application will be recorded on the eCRF and subject diary. The Investigator or designee involved in this step must not be involved in any assessments in order to protect the blind.

6.4.12. Supervised Sunscreen Application

All subjects will undergo supervised sunscreen application. The Investigator or designee will oversee application of the SPF 50 sunscreen. Product application will be recorded on the eCRF and subject diary.

6.5. Visit 5 – 1 day after Visit 4

Subjects will be instructed to arrive at the site prior to 9:00 AM to minimize exposure to intense sunlight.

6.5.1. Current / Concomitant Medication

Any concomitant therapy taken since the last visit and throughout the study will be recorded on the eCRF by the Investigator or designee.

6.5.2. Adverse Events

Adverse events will be assessed by the Investigator or designee and recorded on the eCRF, as per the process detailed in Section 7.

As per Section 7.1, the following does not meet the definition of an adverse event: “Any clinically significant abnormal laboratory findings (if applicable) or other abnormal safety assessments which are associated with the underlying disease, unless judged by the investigator to be more severe than expected for the subject’s

 GlaxoSmithKline	Document Name	eCRF 20 Day Cream.doc		
	Type	Version	Document Identifier	Effective Date
	eldo_controlled	0.0: Current Effective Date	090032d580e2d8a6	07-Jun-2017 01:32:30
	Reason For Issue	Auto Issue		

condition.” Therefore, the Dermatologist (erythema, edema, dryness, and desquamation) and Subject-self assessment (pain, stinging/burning, itching, tightness, redness, and dryness) grades will only be considered adverse events if they are scored as “Severe”, or if the investigator judges them to be more severe than expected in context of the Glycolic Acid treatment procedure.

6.5.3. Continued Subject Eligibility

The Investigator or designee will ascertain whether there have been any deviations from the protocol since the last visit, whether the subject has adhered to the lifestyle restrictions since the last visit and whether, in their opinion, the subject is eligible to continue in the study. Subject Continued Subject Eligibility will be recorded on the eCRF.

6.5.4. Compliance (Diary Review)

Subject diaries will be reviewed by the Investigator or their designee. Subjects who apply the washout products (All subjects) and test product (Group I, only) more or less frequently than twice a day will be considered to have deviated from the protocol and additional/missed applications will recorded on the Deviations Log. The total number of product applications and total number of missed product applications will be recorded on the eCRF.

6.5.5. Washout Products Weighing

The Investigator or designee will weigh the washout products using a calibrated mass balance to 2 decimal places (in grams) and will document the measured weight on the eCRF.

6.5.6. Test Product Weighing

The Investigator or designee will weigh the test product using a calibrated mass balance to 2 decimal places and will document the measured weight on the eCRF.

6.5.7. Instrumental Measurements Post-Procedure, Post-Treatment (48±4 hours after Facial Peel)

Measurements to be taken and recorded as per 6.3.11, 48±4 hours after completion of the facial peel procedure.

6.5.8. Subject Self-Assessment Post-Procedure, Post-Treatment (48±4 hours after Facial Peel)

Assessments to be taken and recorded as per 6.3.13, 48±4 hours after completion of the facial peel procedure.

 GlaxoSmithKline	Document Name	Protocol 2017-01-08-SPF 20 Day Cream.doc		
	Type	Version	Document Identifier	Effective Date
	eldo_controlled	0.0: Current Effective Date: Current	090032d580e2d8a6	07-Jun-2017 01:32:30
	Reason For Issue	Auto Issue		

6.5.9. Dermatologist Assessment Post-Procedure, Post-Treatment (48±4 hours after Facial Peel)

Assessments to be taken and recorded as per 6.3.14, 48±4 hours after completion of the facial peel procedure.

6.5.10. Supervised Test Product Application

Only subjects in Group I will undergo supervised test product application. The Investigator or designee will oversee application of the test product. Product application will be recorded on the eCRF and subject diary. The Investigator or designee involved in this step must not be involved in any assessments in order to protect the blind.

6.5.11. Supervised Sunscreen Application

All subjects will undergo supervised sunscreen application. The Investigator or designee will oversee application of the SPF 50 sunscreen. Product application will be recorded on the eCRF and subject diary.

6.6. Visit 6 – 1 day after Visit 5

Subjects will be instructed to arrive at the site prior to 9:00 AM to minimize exposure to intense sunlight.

6.6.1. Current / Concomitant Medication

Any concomitant therapy taken since the last visit and throughout the study will be recorded on the eCRF by the Investigator or designee.

6.6.2. Adverse Events

Adverse events will be assessed by the Investigator or designee and recorded on the eCRF, as per the process detailed in Section 7.

As per Section 7.1, the following does not meet the definition of an adverse event: “Any clinically significant abnormal laboratory findings (if applicable) or other abnormal safety assessments which are associated with the underlying disease, unless judged by the investigator to be more severe than expected for the subject’s condition.” Therefore, the Dermatologist (erythema, edema, dryness, and desquamation) and Subject-self assessment (pain, stinging/burning, itching, tightness, redness, and dryness) grades will only be considered adverse events if they are scored as “Severe”, or if the investigator judges them to be more severe than expected in context of the Glycolic Acid treatment procedure.

 GlaxoSmithKline	Document Name	090032d580e2d816 20 Day Cream.doc		
	Type	Version	Document Identifier	Effective Date
	eldo_controlled	0.0: CORRECTIVE EFFECTIVE DATE RENEWED	090032d580e2d816	07-Jun-2017 01:32:30
	Reason For Issue	Auto Issue		

6.6.3. Continued Subject Eligibility

The Investigator or designee will ascertain whether there have been any deviations from the protocol since the last visit, whether the subject has adhered to the lifestyle restrictions since the last visit and whether, in their opinion, the subject is eligible to continue in the study. Subject Continued Subject Eligibility will be recorded on the eCRF.

6.6.4. Compliance (Diary Review)

Subject diaries will be reviewed by the Investigator or their designee. Subjects who apply the washout products (All subjects) and test product (Group I, only) more or less frequently than twice a day will be considered to have deviated from the protocol and additional/missed applications will recorded on the Deviations Log. The total number of product applications and total number of missed product applications will be recorded on the eCRF.

6.6.5. Washout Products Weighing

The Investigator or designee will weigh the washout products using a calibrated mass balance to 2 decimal places (in grams) and will document the measured weight on the eCRF.

6.6.6. Test Product Weighing

The Investigator or designee will weigh the test product using a calibrated mass balance to 2 decimal places and will document the measured weight on the eCRF.

6.6.7. Instrumental Measurements Post-Procedure, Post-Treatment (72±4 hours after Facial Peel)

Measurements to be taken and recorded as per 6.3.11, 72±4 hours after completion of the facial peel procedure.

6.6.8. Subject Self-Assessment Post-Procedure, Post-Treatment (72±4 hours after Facial Peel)

Assessments to be taken and recorded as per 6.3.13, 72±4 hours after completion of the facial peel procedure.

6.6.9. Dermatologist Assessment Post-Procedure, Post-Treatment (72±4 hours after Facial Peel)

Assessments to be taken and recorded as per 6.3.14, 72±4 hours after completion of the facial peel procedure.

 GlaxoSmithKline	Document Name	Protocol 2017-01-08F 20 Day Cream.doc		
	Type	Version	Document Identifier	Effective Date
	eldo_controlled	0.0: Current Effective/Current Review	090032d580e2d8a6	07-Jun-2017 01:32:30
	Reason For Issue	Auto Issue		

6.6.10. Supervised Test Product Application

Only subjects in Group I will undergo supervised test product application. The Investigator or designee will oversee application of the test product. Product application will be recorded on the eCRF and subject diary. The Investigator or designee involved in this step must not be involved in any assessments in order to protect the blind.

6.6.11. Supervised Sunscreen Application

All subjects will undergo supervised sunscreen application. The Investigator or designee will oversee application of the SPF 50 sunscreen. Product application will be recorded on the eCRF and subject diary.

6.7. Visit 7 – 4 days after Visit 6

Subjects will be instructed to arrive at the site prior to 9:00 AM to minimize exposure to intense sunlight.

6.7.1. Current / Concomitant Medication

Any concomitant therapy taken since the last visit and throughout the study will be recorded on the eCRF by the Investigator or designee.

6.7.2. Adverse Events

Adverse events will be assessed by the Investigator or designee and recorded on the eCRF, as per the process detailed in Section 7.

As per Section 7.1, the following does not meet the definition of an adverse event: “Any clinically significant abnormal laboratory findings (if applicable) or other abnormal safety assessments which are associated with the underlying disease, unless judged by the investigator to be more severe than expected for the subject’s condition.” Therefore, the Dermatologist (erythema, edema, dryness, and desquamation) and Subject-self assessment (pain, stinging/burning, itching, tightness, redness, and dryness) grades will only be considered adverse events if they are scored as “Severe”, or if the investigator judges them to be more severe than expected in context of the Glycolic Acid treatment procedure.

6.7.3. Continued Subject Eligibility

The Investigator or designee will ascertain whether there have been any deviations from the protocol since the last visit, whether the subject has adhered to the lifestyle restrictions since the last visit and whether, in their opinion, the subject is eligible to continue in the study. Subject Continued Subject Eligibility will be recorded on the eCRF.

 GlaxoSmithKline	Document Name	090032d580e2d8a6 20 Day Cream.doc		
	Type	Version	Document Identifier	Effective Date
	eldo_controlled	0.0; CORRECTED/Effective Date: RENEWED	090032d580e2d8a6	07-Jun-2017 01:32:30
	Reason For Issue	Auto Issue		

6.7.4. Compliance (Diary Review)

Subject diaries will be reviewed by the Investigator or their designee. Subjects who apply the washout products (All subjects) and test product (Group I, only) more or less frequently than twice a day will be considered to have deviated from the protocol and additional/missed applications will recorded on the Deviations Log. The total number of product applications and total number of missed product applications will be recorded on the eCRF.

6.7.5. Washout Products Weighing

The Investigator or designee will weigh the washout products using a calibrated mass balance to 2 decimal places (in grams) and will document the measured weight on the eCRF.

6.7.6. Test Product Weighing

The Investigator or designee will weigh the test product using a calibrated mass balance to 2 decimal places and will document the measured weight on the eCRF.

6.7.7. Instrumental Measurements Post-Procedure, Post-Treatment (168±4 hours after Facial Peel)

Measurements to be taken and recorded as per 6.3.11, 168±4 hours after completion of the facial peel procedure.

6.7.8. Subject Self-Assessment Post-Procedure, Post-Treatment (168±4 hours after Facial Peel)

Assessments to be taken and recorded as per 6.3.13, 168±4 hours after completion of the facial peel procedure.

6.7.9. Dermatologist Assessment Post-Procedure, Post-Treatment (168±4 hours after Facial Peel)

Assessments to be taken and recorded as per 6.3.14, 168±4 hours after completion of the facial peel procedure.

6.7.10. Supervised Test Product Application

Only subjects in Group I will undergo supervised test product application. The Investigator or designee will oversee application of the test product. Product application will be recorded on the eCRF and subject diary. The Investigator or designee involved in this step must not be involved in any assessments in order to protect the blind.

 GlaxoSmithKline	Document Name	GSK-2072372-01-001-SPF 20 Day Cream.doc		
	Type	Version	Document Identifier	Effective Date
	eldo_controlled	0.0; Current/Effective/Reviewed	090032d580e2d816	07-Jun-2017 01:32:30
	Reason For Issue	Auto Issue		

6.7.11. Supervised Sunscreen Application

All subjects will undergo supervised sunscreen application. The Investigator or designee will oversee application of the SPF 50 sunscreen. Product application will be recorded on the eCRF and subject diary.

6.8. Visit 8 – 7 days after Visit 7

Subjects will be instructed to arrive at the site prior to 9:00 AM to minimize exposure to intense sunlight.

6.8.1. Current / Concomitant Medication

Any concomitant therapy taken since the last visit and throughout the study will be recorded on the eCRF by the Investigator or designee.

6.8.2. Adverse Events

Adverse events will be assessed by the Investigator or designee and recorded on the eCRF, as per the process detailed in Section 7.

As per Section 7.1, the following does not meet the definition of an adverse event: “Any clinically significant abnormal laboratory findings (if applicable) or other abnormal safety assessments which are associated with the underlying disease, unless judged by the investigator to be more severe than expected for the subject’s condition.” Therefore, the Dermatologist (erythema, edema, dryness, and desquamation) and Subject-self assessment (pain, stinging/burning, itching, tightness, redness, and dryness) grades will only be considered adverse events if they are scored as “Severe”, or if the investigator judges them to be more severe than expected in context of the Glycolic Acid treatment procedure.

6.8.3. Continued Subject Eligibility

The Investigator or designee will ascertain whether there have been any deviations from the protocol since the last visit, whether the subject has adhered to the lifestyle restrictions since the last visit and whether, in their opinion, the subject is eligible to continue in the study. Subject Continued Subject Eligibility will be recorded on the eCRF.

6.8.4. Compliance (Diary Review)

Subject diaries will be reviewed by the Investigator or their designee. Subjects who apply the washout products (All subjects) and test product (Group I, only) more or less frequently than twice a day will be considered to have deviated from the protocol and additional/missed applications will recorded on the Deviations Log. The total

 GlaxoSmithKline	Document Name	eCRF 20 Day Cream.doc		
	Type	Version	Document Identifier	Effective Date
	eldo_controlled	0.0; Duplicate Effective Date	090032d580e2d8a6	07-Jun-2017 01:32:30
	Reason For Issue	Auto Issue		

number of product applications and total number of missed product applications will be recorded on the eCRF.

6.8.5. Washout Products Weighing

The Investigator or designee will weigh the washout products using a calibrated mass balance to 2 decimal places (in grams) and will document the measured weight on the eCRF.

6.8.6. Test Product Weighing

The Investigator or designee will weigh the test product using a calibrated mass balance to 2 decimal places and will document the measured weight on the eCRF.

6.8.7. Instrumental Measurements Post-Procedure, Post-Treatment (336±4 hours after Facial Peel)

Measurements to be taken and recorded as per 6.3.11, 336±4 hours after completion of the facial peel procedure.

6.8.8. Image Capture (VISIA) Post-Procedure, Post-Treatment (336±4 hours after Facial Peel)

Assessments to be taken and recorded as per 6.3.12, 336±4 hours after completion of the facial peel procedure.

6.8.9. Subject Self-Assessment Post-Procedure, Post-Treatment (336±4 hours after Facial Peel)

Assessments to be taken and recorded as per 6.3.13, 336±4 hours after completion of the facial peel procedure.

6.8.10. Subject Global Self-Assessment

Test subjects will rate the level of satisfaction with the post-procedure skin care regimen to which they were randomized using scale below. These data will be recorded on the eCRF.

Score	Description
0	Very Satisfied
1	Satisfied
2	Poorly Satisfied
3	Not at all Satisfied

 GlaxoSmithKline	Document Name	eCRF 20 Day Cream.doc		
	Type	Version	Document Identifier	Effective Date
	eldo_controlled	0.0: CURRENT/Effective/Current	090032d580e2d8a6	07-Jun-2017 01:32:30
	Reason For Issue	Auto Issue		

6.8.11. Dermatologist Assessment Post-Procedure, Post-Treatment (336±4 hours after Facial Peel)

Assessments to be taken and recorded as per 6.3.14, 336±4 hours after completion of the facial peel procedure.

6.8.12. Dermatologist Global Assessment

The Dermatologist will assess the local tolerance of the post-procedure skin care regimen in context of the expected effects of the procedure for each subject using the scale below and document the score on the eCRF. To make this assessment, the Dermatologist will draw on the total set of clinical and subject self-assessment data for each subject. The Dermatologist must be unaware of whether a subject was randomized to test product to protect the blind.

Rating	Description
0 - Product Regimen was Well Tolerated	No clinically significant worsening of the expected signs/symptoms of the procedure. No new signs/symptoms manifest during product use.
1 - Product Regimen was Not Well Tolerated	Clear, clinically relevant worsening of the severity or frequency of expected signs/symptoms of the procedure and/or any occurrence of new, unexpected signs/symptoms during product use.

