11. Only subjects randomised to Group I will be dispensed test product. Subjects in Group I and II will be dispensed different test diaries to reflect the difference in treatment allocation. The washout diary will be returned at the same time as test diary dispensing.
12. Test product application will occur immediately after the post-procedure, pre-treatment (Baseline) assessments are complete and under the supervision of the Investigator or designee to subjects in Group I, only. Subjects in Group II will not apply anything to their face. The Evaluator must be blind to test product application.
13. Measurements to be taken 180±15 minutes, 360±15 minutes, 24±4 hours, 48±4 hours, 72±4 hours, 168±4 hours and 336±4 hours after completion of the facial peel procedure. At Visit 3, there must be at least 30 minutes between test product application (Group I, only) and instrumental measurements.
14. Images to be captured 24±4 hours after completion of the facial peel procedure and at Visit 8 (Day 22).
15. Assessments to be taken 180±15 minutes, 24±4 hours, 48±4 hours, 72±4 hours, 168±4 hours and 336±4 hours after completion of the facial peel procedure.
16. Test product application will be conducted under the supervision of the Investigator or designee to subjects in Group I, only. Subjects in Group II will not apply the test product to their face.
17. Sunscreen application will be conducted under the supervision of the Investigator or designee to all subjects.

 GlaxoSmithKline	Document Name	Protocol 207213/2013/001F 20 Day Cream.doc		
	Type	Version	Document Identifier	Effective Date
	eldo controlled	0.0: Current Effective/Current	090032d580e2d816	07-Jun-2017 01:32:30
	Reason For Issue	Auto Issue		

PROTOCOL SYNOPSIS FOR STUDY 207213

Brief Summary

This is a randomized, evaluator-blind, single-center and two-arm clinical study designed to evaluate the local tolerance and cosmetic efficacy of a topical skin care formulation in healthy female subjects with moderate to advanced photo-damaged facial skin who have undergone a 70% Glycolic Acid facial peel procedure. It is hypothesized that the test product, which is specifically designed as a moisturizing cream for dry, sensitive skin, will present a favorable local tolerance profile in this population.

Objective(s) and Endpoint(s)

Objective(s)	Endpoint(s)
Primary	

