The following assessments will be conducted in the order written:

1. Current / Concomitant Medication
2. Adverse Events
3. Continued Subject Eligibility

Document Name	090032d580e2d8a6 20 Day Cream.doc		
Type	Version	Document Identifier	Effective Date
eldo controlled	0.0; CORRECTIVE EFFECTIVE	090032d580e2d8a6	07-Jun-2017 01:32:30
Reason For Issue	Auto Issue		

4. Compliance (Diary review)
 5. Washout Products Weighing
 6. Test Product Weighing
 7. Instrumental Measurements Post-Procedure, Post-Treatment*
 8. Image capture (VISIA) Post-Procedure, Post-Treatment*
 9. Subject Self-Assessment Post-Procedure, Post-Treatment*
 10. Subject Global Self-Assessment
 11. Dermatologist Assessment Post-Procedure, Post-Treatment*
 12. Dermatologist Global Assessment of Tolerance
 13. Products and Test Diary Return
 14. Discharge from Study
- * Assessments to be taken 336±4 hours after completion of the facial peel procedure

Type and Planned Number of Subjects

Approximately 130 healthy females within the ages of 30 and 60 years (inclusive) with Fitzpatrick Skin Classification II-IV and moderate to advanced photo-damaged skin will be screened to randomize 80 subjects to ensure approximately 60 subjects (30 subjects per group) successfully complete the study. CCI

With 30 subjects per treatment group, a change from baseline in Transepidermal Water Loss (TEWL) at least half the magnitude of the standard deviation CCI) can be detected at two-sided alpha=0.05 with 80% power.

Main Criteria for Inclusion

Healthy female subjects aged 30-60 years (inclusive) with a Fitzpatrick skin phototype II-IV and Glogau photoaging type II-III will be recruited for this study.

 GlaxoSmithKline	Document Name	090032d580e2d8a6 - Physiogel Calming Relief SPF 20 Day Cream.doc		
	Type	Version	Document Identifier	Effective Date
	eldo_controlled	0.0; CURRENT Effective Date: CURRENT	090032d580e2d8a6	07-Jun-2017 01:32:30
	Reason For Issue	Auto Issue		

Product Information

	Reference / Washout Cleanser	Test Product	Reference / Washout Sunscreen
Product Name	Simple™ Kind to Skin Moisturising Facial Wash	Physiogel Calming Relief SPF 20 Cream	Sunmax Sensitive SPF 50
Product Formulation Code	Not Applicable (Commercial, UK)	CCI [REDACTED]	CCI [REDACTED] (Commercial, Brazil)
Application Quantity	Approximately 0.6-1 grams (g)		
Route of Application	Topical		

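### As worded, the inputs to the primary tolerance rating can include the subject's open-label satisfaction score, and nothing in the plan keeps that score from the blinded evaluator

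*Protocol*

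**What the plan says.** The primary endpoint is the dermatologist's binary global rating of local tolerance at Visit 8. On its inputs, Protocol 6.8.12 says "the Dermatologist will draw on the total set of clinical and subject self-assessment data for each subject". SAP 8.1 repeats the sentence unchanged. Neither place names an item that is left out. The next sentence of 6.8.12 requires that the dermatologist not know the allocation.

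Protocol 6.8.10 is headed "6.8.10. Subject Global Self-Assessment". Its content is satisfaction on a 0–3 scale: "Test subjects will rate the level of satisfaction with the post-procedure skin care regimen to which they were randomized".

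The Visit 8 list in the Protocol Synopsis (repeated in Protocol 3.1) opens with "The following assessments will be conducted in the order written". It places "10. Subject Global Self-Assessment" ahead of the dermatologist's sign scores (item 11) and "12. Dermatologist Global Assessment of Tolerance".

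Subjects know their arm. There is no vehicle control. For the first application after the peel, footnote 12 of the Schedule of Events says "Subjects in Group II will not apply anything to their face". Footnote 11 adds "Subjects in Group I and II will be dispensed different test diaries to reflect the difference in treatment allocation".

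**The concern.** The primary rating is meant to be a blinded clinical judgement about skin. Satisfaction with a regimen is something else. A subject who was given a cream and one who was given none may differ in satisfaction for reasons unrelated to tolerance, and each knows which she is. If the evaluator consults that score, as a literal reading allows, the subject's opinion of her allocation can enter the rating.

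Two results depend on that rating: the success rule in Protocol 9.2.3 (more than half of the test group rated favourably), and the between-group comparison in SAP 8.1 (Chi-square test, difference in proportions and 95% confidence interval).

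**Working it through.** **Reading the passages together**

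1. Scope of the inputs. Protocol 6.8.12 and SAP 8.1 call for all clinical and subject self-assessment data, with no exception.
2. Name of the item. The satisfaction question carries the title of a subject self-assessment, so the literal wording covers it.
3. Timing. It is item 10 and the primary rating is item 12, so the score is already on the eCRF when the rating is made.
4. Source. It comes from a subject who knows her arm.
5. Safeguards. The evaluator is blind to diary review and to product application (Schedule of Events, footnotes 2 and 12). Staff assessing endpoints are blind to randomisation (Protocol 3.4). Staff who dispense or supervise the product may not assess (6.3.21, 6.3.22, 6.4.11). None of these mentions the satisfaction score.

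**The plan's own figure**

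The plan gives no figure for this point. Its one power statement concerns TEWL: 2.1/4 = 0.525 SD with n = 30, two-sided 0.05. A paired t-test then has power 79.4%, against 80% stated. Nothing here changes that.

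**What a shift would do (illustration)**

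The shift sizes and true rates below are assumptions; the documents give neither. Group size is 30 (planned completers) or 40 (80 randomised, if split equally).

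*Unit of change.* One altered rating is 1/40 = 2.5 points, or 1/30 = 3.3 points.

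*Between-group test.* Let the true favourable rate be p in both arms, with recorded ratings in one arm lowered to p − s. The test rejects when (p̂₁ − p̂₂)² / [p̄(1 − p̄)(2/n)] > 3.841. Summing the product of the two binomial probabilities over all rejecting pairs gives:

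| Rated per arm | p | s = 0 | s = 5 points | s = 10 points | s = 15 points |
|---|---|---|---|---|---|
| 40 | 80% | 5.1% | 8.4% | 17.7% | 32.2% |
| 40 | 90% | 5.9% | 11.1% | 24.7% | 43.6% |
| 30 | 80% | 4.9% | 7.3% | 14.2% | 25.3% |
| 30 | 90% | 5.4% | 9.5% | 19.4% | 33.5% |

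*Success rule.* More than 50% means at least 21 of 40, or 16 of 30. The binomial probability of passing is:

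| Recorded rate | n = 40 | n = 30 |
|---|---|---|
| 45% | 0.213 | 0.231 |
| 50% | 0.437 | 0.428 |
| 55% | 0.684 | 0.645 |
| 70% | 0.994 | 0.983 |

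A shift from 45% to 55% would matter a great deal. At a recorded rate of 70% the rule passes almost always, so a true rate of 80% lowered by 10 points would still pass.

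**The case against.** The strongest reply is that the phrase was never meant to cover satisfaction.

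- Where the protocol spells out subject self-assessment, for example in the adverse-event text of 6.2.2 to 6.8.2, it lists six symptoms. The scoring form in 6.3.13 holds only those six.
- The global item is a separate row in the Schedule of Events and a separate endpoint in Protocol section 2.
- Protocol 9.2.5 bases secondary tolerance on self-assessment scores at each visit, whereas satisfaction is collected once.
- SAP 8.3 treats satisfaction under other analyses, and SAP Appendix 2 tabulates it on the ITT population. SAP 5.1 puts the tolerance assessments on the Safety population.
- Both anchors of the rating scale refer only to signs and symptoms, so satisfaction is not a criterion for choosing 0 or 1.

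It can also be said that a fixed order is not disclosure: 6.8.10 says only that the score goes on the eCRF.

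Most of this stands. The narrower reading is credible and may be what the sponsor intended. It does not settle the matter, because the sentence that governs the primary rating asks for everything, and nothing there or elsewhere takes this item out. Two evaluators could follow the text in good faith and use different inputs.

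**Conclusion.** The point holds as an ambiguity in how the primary endpoint is formed. A literal reading admits an unblinded, arm-related opinion into the rating, and no passage prevents it. Its size is unknown. It depends on whether the evaluator looks at the score, how far satisfaction follows the arm, and how many ratings would change. The between-group comparison is the part most exposed. The success rule is at risk only if the true favourable rate is near 50%.

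A reader might infer more than the documents support:

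- *That the plan breaks the evaluator's blind.* The score does not state the arm, both arms rate a regimen, and both use cleanser and sunscreen. Allocation could only be guessed. Influence through opinion is the better-founded concern.
- *That the item 11 sign scores are affected as well.* Section 6.8.11 follows 6.3.14, which rates the facial skin as seen at that moment and does not draw on subject data.
- *That 2.5 points is the bias.* It is only one subject out of 40, and says nothing about how many ratings would move.

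**What to change.** In Protocol 6.8.12 and SAP 8.1, add that subject self-assessment data means the six symptom scores, and that the 6.8.10 satisfaction score is not available to the evaluator before the global tolerance rating is recorded. Leave the other clinical data in use: sign scores, adverse events without fields that would reveal allocation, and the VISIA images. Protocol 6.1.1 says the images are taken to support the evaluator's global tolerance assessment, so a closed list of scores alone would wrongly drop them.

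To put this into practice, either withhold the score from the evaluator or move item 10 after item 12 in the Visit 8 order (Synopsis, 3.1 and 6.8).

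The cost is a clause in each document and, if chosen, a reordering at one visit. No assessment, subject or sample-size figure changes. There are two small limits. If the item is moved, subjects rate satisfaction after the dermatologist's assessment, which could colour a secondary endpoint; withholding the score avoids this. And the six symptom scores still come from unblinded subjects, so the change removes one avoidable route of influence, not all of them.
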